#### 2.1.4 Setting

Phase 1 of the study will take place in a minimum of four NHS secondary care hospitals, in one or more surgical specialties (section 5.5). A Principal Investigator (PI), (consultant surgeon from one of the surgical specialties, consultant in perioperative medicine, or physiotherapist with expertise in IMT) will be appointed from each hospital. A small number of research nurses or physiotherapists from each hospital will be trained and deliver the intervention to all participants recruited. In Phase 2 recruitment will be extended to a further two or more centres.

#### 2.2 Randomisation

Randomisation will be carried out after eligibility has been confirmed and consent given, and baseline measurements have been made. Randomisation will be performed by an authorised member of the local research team using a secure internet-based randomisation system ensuring allocation concealment. Participants will be randomised in a 2:1:1 ratio to: i) high resistance IMT ii)

low resistance IMT or iii) usual care (no IMT and written instructions on deep breathing exercises). The random allocation will be stratified by centre and specialty, so that each speciality at each centre will have approximately equal numbers of participants allocated to the high resistance IMT group and low resistance IMT group/usual care. As the study is not evaluating the surgery per-se, surgical experience is not a criterion for participation (all participants will be under the care of a consultant surgeon). In the context of this study, clustering by surgeon is not relevant to the sample size and can be ignored (on the basis that the intraclass correlation is negligible; personal communication with [name] for a previous study).

#### 2.3 Framework

The main aim of the study is to compare the number of lung complications between the three groups in the first 30 days after surgery. We will record whether a lung complication develops in hospital whilst patients are recovering from surgery or causes hospital admissions after patients are discharged from hospital following their operation. We will also compare the time patients spend in hospital, their quality of life after their operation and survival.

The study will be conducted in two phases, Phase 1 (pilot) and Phase 2 (main study). In Phase 1, we will determine whether we can recruit participants in the study and whether they perform their exercises as instructed. We also will evaluate (in participants receiving high intensity IMT only) whether either of two interventions: (A) an additional 'virtual' follow up meeting conducted via telephone or video call; (B) using the algorithm built into the POWERbreathe K-series to estimate maximal inspiratory pressure (MIP) and increase device load automatically; improves adherence to IMT and results in more participants performing the IMT exercises correctly. If Phase 1 shows that we can recruit enough participants according to our progression criteria (section 5.2.6) and that they can perform their exercises as instructed in the protocol, we will move to Phase 2.

#### 2.4 Sample size

#### 2.4.1 Study sample size

We will recruit 2,500 participants (1250 high resistance IMT, 625 low resistance IMT and 625 usual care), providing 90% power to detect a 5% difference in the primary outcome (of any PPC versus no PPC; 20% vs 15%, risk ratio 0.75) between high resistance IMT versus low resistance IMT and usual care combined. We do not anticipate a difference between the low resistance IMT and usual care groups and will be able to quantify a zero difference with a 95% CI of width +/-4.5%. In addition, the study will have 75% (90%) power to detect a difference of 15% (14%) versus 20% between the high intensity and low intensity groups, or between the high intensity and usual care groups.

#### 2.4.2 SWAT Sample size

It is planned to recruit 160 participants to the high intensity IMT during Phase 1; 40 per each of the four treatment combinations. The SWAT will provide 95% confidence intervals of width +/- 0.31 standard deviations in progression of training load for the main effects of visit and method load adjustment and 95% confidence intervals of width +/- 0.45 standard deviations for comparisons between load method when an extra visit is included and separately between load method when an extra visit is not included.

## 2.5 Blinding

The study includes a low resistance IMT intervention group, set to a resistance level that is considered ineffective in influencing MIP [27]. This group has been included so that participants,

their clinical care team (i.e. surgeon, anaesthetist and post-operative care team) and all members of the research team with the exception of those administering the IMT interventions can be blind to participants' allocation to high/low resistance IMT. The research nurses or physiotherapists administering the low and high resistance IMT interventions will obtain the allocation from the internet system and will not be blind to allocation.

Some participants in the low resistance IMT group may discern that they are not doing the 'real' IMT intervention, since their training load will be constant (i.e. will not increase) throughout the intervention period. However, the risk of unblinding is reasonably low since surgical patients are unlikely to be familiar with the concept of IMT and so will not know what real IMT feels like. Furthermore, there have been no side effects reported from performing IMT in various patient populations, so patients are unlikely to be unblinded because of any side effects attributed to IMT. Care will be taken to prevent the opportunity for conversation between participants allocated to low and high resistance IMT to avoid the risk of contamination.

The PIL and the process of informed consent will describe the study in terms of testing different types of 'breathing exercises' (with and without a device) and explain the uncertainty around the potential beneficial effects of these exercises. Therefore, the participant should not have a strong expectation that one or other types of breathing exercises should lead to fewer complications after surgery. Participants will be made aware before entering the study that the study involves breathing exercises performed with a device (IMT) or without a device but they will not be told specifically that there are high and low resistance IMT training groups. The unique code provided by the randomisation system will provide the intervention as specified according to the predetermined randomisation list drawn up by the study statistician prior to recruitment. The allocations will only be known by individuals administering the interventions and the study statistician responsible for generating the allocation scheme and for producing unblinded analyses and will not be disclosed to any other member of the research team.

## 3. Populations

#### 3.1 Study populations

We will recruit participants undergoing major elective cardiac surgery (on the heart and great vessels carried out via a midline sternotomy); thoracic surgery (open or minimal access surgery on the lungs and surrounding tissues); or abdominal surgery (open or minimal access surgery within the abdominal cavity/intraperitoneally); (oesophageal, gastric, hepatobiliary, colorectal, gynaecological, urological, or open aortic aneurysm repair). These patient populations have been chosen because they have a high incidence of PPCs [1, 2]. We will include both open and laparoscopic (including robotic) surgery for generalisability, as a significant proportion of abdominal surgery is conducted laparoscopically.

We will include only participants at high risk of PPCs (20% incidence) identified using the ARISCAT score as shown in Figure 1 (≥26; based on age, arterial oxyhaemoglobin saturation by pulse oximetry, respiratory infection in previous month, preoperative anaemia (Hb ≤10 g/dl), site of surgical incision, > 2hr predicted duration of surgery [1]). These components are easily assessed preoperatively and will be available for most participants at the time of recruitment. The ARISCAT score has been validated in our participant population [2].

Figure 1: The seven ARISCAT predictors of risk of PPCs

	β Regression Coefficients	Score
Age (yr)		
≤50	0	0
51–80	0.331	3
>80	1.619	16
Preoperative Spo 2		
≥96%	0	0
91–95%	0.802	8
≤90%	2.375	24
Respiratory infection in the	last month	
No	0	0
Yes	1.698	17
Preoperative anemia (Hb ≤	10 g/dl)	
No	0	0
Yes	1.105	11
Surgical incision		
Peripheral	0	0
Upper abdominal	1.480	15
Intrathoracic	2.431	24
Duration of surgery (h)		
<2	0	0
2–3	1.593	16
>3	2.268	23
Emergency procedure		
No	0	0
Yes	0.768	8

\*Three levels of risk were indicated by the following cutoffs: <26 points, low risk; 26–44 points, moderate risk; and  $\geq$ 45 points, high risk.

 $\begin{array}{lll} \text{ARISCAT} &=& \text{Assess} & \text{Respiratory} & \text{Risk} & \text{in Surgical Patients in Catalonia;} \\ \text{Hb} &=& \text{hemoglobin;} & \text{SpO}_2 =& \text{arterial oxyhemoglobin saturation by pulse oximetry.} \\ \end{array}$ 

#### 3.1.1 Inclusion criteria

Participants may enter the study if ALL of the following apply:

- 1. Age ≥18
- 2. Elective major cardiac, thoracic and abdominal surgery (oesophageal, gastric, hepatobiliary, colorectal, gynaecological, urological, or open aortic aneurysm repair) under general anaesthesia, including both open and laparoscopic surgery
- 3. ARISCAT score ≥26 [1]
- 4. At least 14 days until planned operation date
- 5. Able to give informed consent

NB: Participants who fulfil each of the criteria listed above and are undertaking a prehabilitation programme as part of usual care at their hospital **can** be included in the study.

#### 3.1.2 Exclusion criteria

Participants may not enter the study if ANY of the following apply:

- 1. Emergency surgery
- 2. Unable to participate in the intervention (e.g. have cognitive impairment)
- 3. Lack capacity to consent
- 4. Recent cardiac, thoracic or open abdominal surgery (in previous 2 months)
- 5. Prisoners
- 6. Patients with a history of spontaneous pneumothorax (if a patient has had a traumatic pneumothorax and are fully recovered, then they can be included)
- 7. Eardrum perforation within 6 weeks
  - 8. Phrenic nerve palsy

#### 3.2 Data sources

Outcome data will be collected using a purpose-designed database. Where the trial database is the site of original recording this will be considered source data. Data will be captured at several timepoints including screening, from admission for surgery to discharge and followed-up for up to 6 months.

Where the database isn't the original recording the source data will include, but is not limited to medical history, medication records, vital signs, physical examination records, and questionnaire responses.

Table 2 Data collection schedule

Data item	Baseline (Pre- randomisation)	Initial training visit* High/low resistance IMT/usual care groups	Additional virtual follow up High resistance IMT group: Phase 1 only	Pre- surgery	In hospital	Discharge	3 months post- surgery	6 months post- surgery
Socio-demographic details	✓							
Co-morbidities	✓							
Routine CPET parameters#				✓				

Maximal inspiratory pressure (MIP)		✓		✓				
Spirometry		✓		✓				
Check on adherence and progression of the IMT training load §			~	4				
Routine clinical measures	✓	✓		✓	✓	✓		
PPCs					✓	✓	✓	✓
Resource use schedule					✓	✓	*	✓
SF-12	✓			✓			✓	✓
EQ-5D-5L	✓			✓			✓	✓
MUST & PONS assessments				✓				
DASI questionnaire	✓							✓
HADS, CDRQ & self- efficacy questionnaires	*							✓
Surgical regret questionnaire								✓
Adverse events			✓	✓	✓	✓		
Serious adverse events			✓	✓			4	✓

\* High resistance IMT/low resistance IMT training can be at POA appointment if more than 2 weeks before surgery. An additional visit will need to be booked if POA appointment is less than 2 weeks before surgery.

#### 3.3 Analysis populations

#### 3.3.1 Intention-to-treat population

Analyses and summaries will be performed on an intention-to-treat basis. Analyses will use data from all participants randomised. The ITT population will consist of all randomised participants, included according to their randomised allocation, regardless of whether they are ineligible, prematurely discontinue treatment or are otherwise protocol deviators.

#### 3.3.2 Per-protocol population

An analysis of the primary outcome on the per-protocol population will be considered if there are a considerable number of major protocol deviators (>5% of the ITT analysis population).

The following types of protocol deviation will be considered:

- Participant did not meet the study eligibility criteria but was treated in the study
- Participant did not receive/adhere to allocated intervention

Note, it may be possible for participants to be classified as a protocol deviation for more than one reason.

The frequency of each type of deviation will be tabulated by treatment allocation (see Table A8).

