#### Sample size calculation

We will recruit 2,500 participants (1250 high resistance IMT, 625 low resistance IMT and 625 usual care), providing 90% power to detect a 5% difference in the primary outcome (of any PPC versus no PPC; 20% vs 15%, risk ratio 0.75) between high resistance IMT versus low

INSPIRE Protocol Version 2.0 resistance IMT and usual care combined. We do not anticipate a difference between the low resistance IMT and usual care groups and will be able to quantify a zero difference with a 95% CI of width +/-4.5%. The sample size required to achieve 80% and 90% power, assuming 5% statistical significance and a two sided test, for target differences of 8%, 5% and 3% are shown in Table 2. The primary outcome of any PPC (vs no PPC); assuming a PPC rate of 15% in the high resistance group and a PPC rate of 20% in the low resistance and usual care groups combined. In addition, the study will have 75% (90%) power to detect a difference of 15% (14%) versus 20% between the high intensity and low intensity groups, or between the high intensity and usual care groups.

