#### 2.1.3 Main study (Phase 2)

Progression criteria from Phase 1 to Phase 2:

- all centres participating in the pilot are recruiting (in one or more specialties);
- at least 40% of eligible patients are consenting to randomisation;
- each centre recruiting >8 patients/month (from any specialty);
- interventions are delivered according to the protocol in all centres;
- the allocated intervention is initiated in >=90% of randomised participants;
- >=70% of patients randomised to high resistance IMT or low IMT adhere to allocated interventions (adherence will be recorded electronically by the IMT device); we will define a patient as adherent with the intervention if they use the IMT device at least five days a week (for a minimum of 30 breaths per day).

If progression criteria are met, recruitment will continue at the Phase 1 hospitals and we will begin recruitment at a minimum of an additional two hospitals (depending on how recruitment is going in Phase 1). Delivery mode of the intervention will be based on the findings in Phase 1 and any amendments to the study will be submitted for approval by the regulatory authorities.

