#### Adherence to inspiratory muscle training

The success of IMT will be defined by the adherence of participants to the intervention.

New variable	Rules
IMT adherence	
 
YES:
 
>= 1 IMT session initiated on >= 5 days / week during >= 2 weeks after randomisation AND
 
>= 30 breaths overall completed on each day
 

	
 
< 1 IMT session initiated on >= 5 days / week during >= 2 weeks after randomisation OR
 
>= 1 IMT session initiated on < 5 days / week during >= 2 weeks after randomisation OR
 
>= 1 IMT session initiated on >= 5 days / week during < 2 weeks after randomisation OR
 
>= 30 breaths overall completed on each day
 

	MISSING: otherwise

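### The per-protocol rule can drop non-adherers from the two device arms but not from usual care, so that supplementary comparison is at risk of selection bias

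*SAP*

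**What the plan says.** SAP 3.3.1 makes intention to treat the basis of analysis. SAP 3.3.2 adds that a per-protocol analysis of the primary outcome will be considered "if there are a considerable number of major protocol deviators (>5% of the ITT analysis population". It names two kinds of deviation: treated despite failing the eligibility criteria, and "Participant did not receive/adhere to allocated intervention". It neither defines a major deviation nor says how adherence is judged in each arm.

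The only adherence variable is in SAP 4.3, under Adherence to inspiratory muscle training (IMT), introduced by "The success of IMT will be defined by the adherence of participants to the intervention". It counts device sessions per week and breaths per day. The progression criterion in SAP 2.1.3 likewise asks that at least 70% of "patients randomised to high resistance IMT or low IMT adhere to allocated interventions". The Protocol's Trial summary describes monitoring of training in the high and low resistance groups, and its Data collection section names the device and the patient diary as sources. Usual care (Protocol 5.6.7) consists of advice and a leaflet, with no record described of whether the exercises were done.

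SAP 4.4.1 sets the primary comparison as high resistance against low resistance and usual care combined.

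**The concern.** A per-protocol comparison is hard enough to interpret when every arm is filtered by the same rule. Here the adherence filter acts on the whole high resistance arm, on half of the pooled comparator (low resistance) and not at all on the other half (usual care). If participants who keep up training before major surgery differ in PPC risk from those who do not, the high resistance arm is enriched for the first kind more than its comparator is. A difference can then appear with no effect of training.

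After early closure, SAP 4.4.3 models only the primary outcome of the trial and that of the study within a trial (SWAT). A per-protocol result on the main outcome would therefore be one of very few comparative estimates reported, and readers would set it beside the intention-to-treat result.

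**Working it through.** **Inputs from the documents**
- Design: "We will recruit 2,500 participants (1250 high resistance IMT, 625 low resistance IMT and 625 usual care", i.e. 2:1:1.
- Target: "providing 90% power to detect a 5% difference in the primary outcome", with "20% vs 15%, risk ratio 0.75", "assuming 5% statistical significance and a two sided test".
- Adherence benchmark in the device arms: 70% (SAP 2.1.3).
- Expected Phase 1 size: about 321 (SAP 2.1). The final number is not given.

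**Assumed, not in the documents:** the ratio r of PPC risk in non-adherers to that in adherers, varied from 0.67 to 2.0.

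**The plan's own figure.** The two-proportion formula with continuity correction for 15% v 20%, two-sided 5% and 90% power gives 1,252 per group, or 2,504 in total, against the stated 2,500. Without the correction it gives 2,424. The event rates and arm sizes used below are therefore the plan's own. The plan states no size for the per-protocol set.

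**Trigger.** The device arms hold 75% of participants. If every non-adherer counts as a deviator, the threshold is passed when 0.75 × f > 0.05, i.e. f > 6.7%, where f is device-arm non-adherence. At the benchmark, f = 30%, so 0.75 × 0.30 = 22.5% of the intention-to-treat set.

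**Filter at f = 30%, N = 2,500.** High: 0.30 × 1,250 = 375 excluded (30%). Low: 0.30 × 625 = 187.5 excluded (30%). Usual care: 0 excluded for non-adherence. Pooled comparator: 187.5/1,250 = 15%. This leaves 875 v about 1,062.

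**Spurious difference with no true effect.** Each arm has 20% risk overall.
- Adherer risk: a = 0.20 / [(1 - f) + f × r]. This is the per-protocol risk in the high arm.
- Pooled comparator: [(1 - f) × a + 0.20] / (2 - f), since low resistance and usual care are of equal size.
- Difference: (a - 0.20) / (2 - f).

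For f = 0.30 and r = 1.5: a = 0.20/1.15 = 17.4%; comparator = (0.7 × 17.4% + 20%)/1.7 = 18.9%; difference -1.5 points.

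| r (assumed) | High | Pooled | Difference (points) | Chance of a significant false benefit, N = 2,500 | Same, N = 321 |
|---|---|---|---|---|---|
| 0.67 | 22.2% | 20.9% | +1.3 | below 2.5% | 1.4% |
| 1.00 | 20.0% | 20.0% | 0 | 2.5% | 2.5% |
| 1.25 | 18.6% | 19.4% | -0.8 | 6.7% | 3.6% |
| 1.50 | 17.4% | 18.9% | -1.5 | 13.9% | 5.0% |
| 2.00 | 15.4% | 18.1% | -2.7 | 35.9% | 8.3% |

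The last two columns use a normal approximation; the nominal value in this direction is 2.5%.

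**Other adherence levels.** For r from 1.25 to 2.0, the difference runs from -0.3 (90% adherent, r = 1.25) to -4.1 (54% adherent, r = 2.0). The 54% is the share completing at least 80% of sessions in the earlier home-based trial cited in Protocol 2.4.

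**Source of the bias.** With equal adherence and the same r in both device arms, high v low is unbiased, and the distortion comes wholly from unfiltered usual care. If adherence were 70% in the high arm and 90% in the low arm, the pooled difference would be -1.16 to -3.75 points, and high v low would also be distorted (-0.91 to -2.80). Table A8 has a training-intensity deviation for the high resistance group only, which could produce such an imbalance.

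**Against sampling error.** At N = 321, 70% adherence leaves about 112 v 136. For r = 1.5 the 95% half-width is 1.96 × √(0.174 × 0.826/112 + 0.189 × 0.811/136) = 9.6 points, more than six times the 1.5-point bias.

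**A randomisation-based alternative.** With no true effect the expected intention-to-treat difference is 0, so dividing it by 0.70 also gives 0, whatever r is.

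**The case against.** **Status of the analysis.** It is conditional and supplementary. SAP 1.1.2 says Sections 1 to 3 reflect the original design. Section 4 plans no per-protocol model, 4.5.6 lists no further exploratory analyses, and Table A11 has no per-protocol column. This stands as a limit on importance. But 3.3.2 remains in the current SAP without a note that it has lapsed, and it points to Table A8, which already uses the cardiac/non-cardiac grouping adopted after the halt (SAP 4.5.2).

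**Exclusions in usual care.** A reader might infer that only device-arm participants can be removed. The documents do not support that: the same bullet covers not receiving the intervention, and Table A8 has lines for cross-over and for ineligible participants. The asymmetry concerns non-adherence. Nor does 3.3.2 formally link to the adherence variable in 4.3, though no other definition is offered. Tabulating deviations by arm would make unequal exclusion visible, but would not remove the selection.

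**Direction.** A reader might infer that the per-protocol result would favour high resistance training. The documents give no relation between adherence and PPC risk. Training load depends on tolerability and training may stop after a serious adverse event, which suggests sicker non-adherers. Yet adherence requires at least two weeks of training, heart surgery patients may wait longer, and an intrathoracic incision carries the highest incision score, which could point the other way. Adjustment for centre and specialty (SAP 4.4.2) would remove only the part of the relation that runs through those factors.

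**Size.** The 54% comes from a stricter measure than this trial's rule of five days a week and 30 breaths a day, so the -4.1 end does not transfer directly. The 5-point target belongs to the 2,500-participant design. Both criticisms stand.

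**Conclusion.** The point holds as a risk of bias in a supplementary analysis. If the per-protocol analysis is run with the listed exclusions, the primary comparison is filtered unequally: about 30% against 15% at 70% adherence. The trigger is likely to be met, provided non-adherers count as major deviators. Under the null the spurious difference at that adherence is -0.8 to -2.7 points for assumed ratios of 1.25 to 2.0, zero at 1 and about +1.3 at 0.67. These figures assume 20% risk in every arm, equal adherence and the same ratio in both device arms, and no covariate adjustment.

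It would be wrong to conclude that the trial's main result is compromised: intention to treat is untouched. At about 321 participants the bias is also small beside sampling error, although its expected size does not shrink with the sample.

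**What to change.** 1. In SAP 3.3.2, define the per-protocol set explicitly and limit its exclusions to deviations that can be ascertained in all three arms, such as ineligibility. Report exclusions by arm.
2. Before adherence is used anywhere, correct the non-adherent rule in SAP 4.3. As printed, it repeats the condition of at least 30 breaths from the adherent rule, joined by OR, so a participant can meet both.
3. Address adherence with a complier-average causal effect for high resistance v the pooled comparator, labelled supplementary and exploratory: the intention-to-treat risk difference divided by the between-arm difference in the proportion receiving adherent high resistance training. Use the difference, not the high-arm proportion alone, because Protocol 5.6.4.1 allows that usual-care participants might obtain a device.

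The cost is SAP wording and one short analysis. The interval widens: with 70% adherent in the high arm and none in the comparator, by a factor of about 1/0.70 = 1.43. The estimate also assumes that training below the adherence threshold has no effect. That must be stated, because Protocol 2.4 describes a dose-response relationship; if partial training helps, the estimate is too large.
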